Creatine is a tripeptide composed of arginine, methionine, and glycine, which can be synthesized by the body or taken from food. Creatine is a naturally occurring amino acid derivative in the human body. Creatine supplementation can improve lean body mass and muscle function, rapidly increase muscle strength, accelerate fatigue recovery, and improve explosive power. Therefore, creatine is widely used in exercise supplement and sarcopenia treatment [21]. Studies have shown that both short-term and long-term supplementation (30 g/day for 5 years) is safe and well tolerated for healthy individuals and many patients from infants to the elderly, and that low dose creatine intakes (e.g., 3 g/day) can provide

significant health benefits [21]. Many animal studies have confirmed the beneficial effect and mechanism of creatine in the cachexia of tumor [22, 23]. However, in clinical studies, the sample size is small and high-quality evidence is lacking. A randomized double-blind controlled trial in which 30 patients with stage III or IV colorectal cancer were selected to receive creatine versus placebo showed more significant improvements in phase Angle and grip strength in the creatine supplement group, but no significant effects on body composition and body weight [24]. Another study on head and neck cancer showed a significant increase in lean body mass from baseline in the creatine supplement group, but no significant difference in the control group. In addition, skeletal muscle strength was also improved in the creatine group, but there was no statistical difference between the two groups [25]. So far, there have been few relevant studies. Although the optimal creatine supplement scheme is not yet clear, it has been reported that creatine supplement of 3-5g/d can make the body reach the saturation level of creatine [9, 26]. In addition, other studies have found that creatine may enhance the invasion and metastasis of some cancers, including colorectal cancer, pancreatic cancer, and breast cancer [27], which is a problem that researchers need to pay attention to.

To sum up, although curcumin partially increases muscle mass, studies have found that curcumin is more likely to be anti-inflammatory and prevent adipose tissue decomposition, while creatine mainly improves lean body mass and muscle function. Therefore, whether the combination of the two can play a more stable synergistic effect in the treatment of cachexia is the main content of this study.

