Group B control group: In addition to the above basic nutrition, oral creatine powder 5g qd, curcumin capsule 2g bid for one month.

The intake, complications and survival of the patients were followed up by telephone for 1 and 3 weeks, physical indicators, nutritional assessment, FAACT and QoL scale were followed up for 2 weeks in the hospital and outpatient department, and nutritional serum indicators, body composition indicators, inflammatory metabolism indicators, physical indicators, nutritional assessment were reviewed for 4 weeks. Evaluation of effect. The long-term survival, re-hospitalization and hospitalization expenses were investigated 3 months later. To evaluate the effect of creatine combined with curcumin on improving the nutritional status, metabolic level and clinical prognosis of alimentary tract neoplasm. Note: Weight is calculated by standard weight: Standard weight (kg) = height (cm)-105.

(3) Combination of drugs

During the study period, patients may have been treated with chemotherapy drugs and immunotherapy drugs due to tumor treatment and may have taken megestrol orally against the oxalic fluid to improve appetite. To avoid the influence of the two groups of therapeutic drugs, the diseases, and drugs of the two groups will eventually be grouped and stratified to eliminate the interference of combined drug use.

(4) Safety evaluation index

- ① Incidence and severity of side effects
- ② The rate of unplanned rehospitalization.

6. Observation of adverse events

Adverse Event (Adverse Event): An adverse medical event occurs after a patient or clinical trial subject receives a drug or a formula for a special medical use, but there is not necessarily a causal relationship.

Serious Adverse Event: An event occurs during the clinical trial that requires hospitalization, prolongates the hospital stay, causes disability, affects the ability to work, threatens life or death, or

results in congenital malformations.

Adverse reaction: an adverse reaction that is harmful rather than expected but is causally related to the application of a drug or special medical use formula food during normal application of the drug or special medical use formula food at prescribed doses. In clinical trials for a new use, all reactions that are harmful and not causally related to the use of a drug or a formula for special medical use, as expected, should be considered adverse when the dose has not been determined.

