Any adverse events that occur during the test should be recorded in detail.

(1) Large dose of creatine supplement may cause muscle stiffness, spasm and other adverse phenomena.

(2) Exceeding recommended doses of curcumin can cause nausea and even vomiting and diarrhea.

None of the doses used in this study exceeded the recommended dose, so the probability of adverse events was small. Once adverse events occur, the oncologist and nutritionist will be reported immediately, and the current intervention will be suspended according to the actual condition of the patient, and the treatment measures will be developed.

7. Research on quality control and quality assurance

(1) Laboratory quality control measures

The standard operating procedures and quality control procedures for experimental observation indicators should be established in hospital laboratories.

(2) Training of researchers

Prior to the commencement of clinical trials, the investigator should be trained in the protocol.

(3) Measures to improve subject compliance

① The researcher should carefully perform informed consent so that the subjects can fully understand the test requirements and cooperate with the test.

(2) Pay attention to the number of days of experimental drugs, whether there is intermittent drug use, and monitor the compliance of subjects.

Compliance = actual number of days of medication/number of days of medication × 100%

Compliance is 80% ~ 120% compliance is good; Compliance is poor if less than 80% or more than 120%.

(4) Oversight of clinical trials

Monitoring of patients' actual nutrient intake during nutritional therapy:

Follow-up: The patients were discharged from the hospital for routine dietary guidance, with daily total energy set at 30-35kcal /kg.d and daily protein intake at 1.0-2.0 g/kg.d, and continued to receive total nutrition preparations and/or whey protein oral nutrition supplement or tube feeding enteral nutrition supplement.

Monitoring of patients' condition during the experiment:

When the patients included in the study experience changes or even adverse reactions, strict diagnosis and treatment will be taken immediately to avoid the occurrence of adverse events.

8. Data security audit

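### Section 6 defines an adverse reaction in two incompatible ways, safety index 1 is undefined, and the plan specifies no by-group comparison of adverse events

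*Combined protocol and SAP*

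**What the plan says.** Section 6 (Observation of adverse events) defines three terms. An adverse event is a harmful medical occurrence after a drug or special medical formula, "but there is not necessarily a causal relationship". A serious adverse event is defined by outcome. An adverse reaction gets two sentences:

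- The first describes "an adverse reaction that is harmful rather than expected but is causally related to the application of a drug" or a special medical formula food, at prescribed doses.
- The second concerns trials of a new use. It says that "all reactions that are harmful and not causally related to the use of a drug or a formula for special medical use" "should be considered adverse when the dose has not been determined".

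Section 5(4) lists two safety indices: "Incidence and severity of side effects" and "The rate of unplanned rehospitalization". Neither section 5(4) nor section 6 defines a side effect. The Summary, in its own row on the safety evaluation index, uses the term when discussing creatine and curcumin. It says side effects are not generally expected at the doses used, and that researchers will still watch for them.

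On recording, section 6 states: "Any adverse events that occur during the test should be recorded in detail". Section 8 repeats the requirement, adds follow-up to resolution or stability, and has the principal investigator review all adverse events cumulatively. Section 9 names a t-test and one-way ANOVA and no method for proportions.

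**The concern.** Two defects meet here. The reaction definition requires causality in one sentence and counts its absence in the next, so an event judged unrelated is excluded by one and admitted by the other. The first safety index then uses a term that is tied to none of the defined categories.

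This matters because of who is enrolled. Patients are receiving radiotherapy, chemotherapy or immunotherapy. The effects the protocol names for curcumin at high intake are nausea, vomiting and diarrhoea, which cancer treatment can also cause. The study is open, and section 6 tells investigators that adverse events are unlikely at these doses. An index that counts only what an unblinded investigator attributes to the products depends on that expectation. It also has no background rate from group A against which to read group B. What is at stake is whether the trial can report how often these symptoms occurred with and without the products.

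**Working it through.** The plan states no figure on this point, so there is none to reproduce. The check is mainly of the text.

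**Step 1. Does each safety term require a causal judgement?**

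| Term | Section | Causal relation required? |
|---|---|---|
| Adverse event | 6 | No |
| Adverse reaction, first sentence | 6 | Yes |
| Adverse reaction, second sentence (new use, dose not determined) | 6 | Counts those *not* related |
| Side effect (index 1) | 5(4) | Not stated; the Summary uses it for the two study products |
| Unplanned rehospitalization (index 2) | 5(4) | No |

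Rows 2 and 3 conflict. The wording on expectedness is also garbled: the first sentence sets harm against what is expected, while the second carries a stray reference to what is expected.

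**Step 2. When does the second sentence apply?** Only when the dose has not been determined. Section 1.2.3 says "Although the optimal creatine supplement scheme is not yet clear", whereas section 6 relies on the doses being within what is recommended, and the protocol states an amount for each product. The remark in 1.2.3 concerns creatine only. The documents do not settle whether the condition is met.

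**Step 3. What does index 1 give in each group?**

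- If side effects means effects of creatine and curcumin (the Summary's use), group A takes neither product and contributes no count.
- If it means effects of any drug or formula (the scope of section 6), chemotherapy nausea counts in both groups.
- If it means adverse events, everything counts in both groups.

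**Step 4. How many patients could be affected?** The documents give no rate, so assume that 30% to 60% of patients have nausea, vomiting or diarrhoea within a month. With 76 per group (section 3), 0.30 × 76 = 22.8 and 0.60 × 76 = 45.6, or about 23 to 46 patients per group. With the 68 per group left after the planned loss, 0.30 × 68 = 20.4 and 0.60 × 68 = 40.8. At one extreme, if every such event in group B is judged unrelated to the products, an attribution-based index reports 0. At the other, an all-event index reports about 23 to 46.

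**Step 5. What could an all-event comparison detect?** For n = 76 per group and two-sided alpha 0.05, with p̄ the mean of the two proportions:

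power = Φ{ [ |p_B − p_A| − 1.96 √(2p̄(1−p̄)/n) ] / √[ (p_A(1−p_A) + p_B(1−p_B))/n ] }

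Example: p_A = 0.10, p_B = 0.277, p̄ = 0.1885. The first root is √(0.3059/76) = 0.0634, and 1.96 times it is 0.1244. The second is √(0.2903/76) = 0.0618. Then (0.177 − 0.1244)/0.0618 = 0.85 and Φ(0.85) ≈ 0.80.

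| Assumed incidence in A | Incidence in B for 80% power |
|---|---|
| 5% | 20% |
| 10% | 28% |
| 20% | 41% |
| 30% | 52% |

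The comparison is feasible, but only large differences would be detected reliably, so an estimate with its interval will tell more than a test.

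**The case against.** The strongest reply is that the safety data will exist and the defect is one of wording. The adverse-event definition is free of causality. Sections 6 and 8 require every adverse event to be recorded, and section 5(2) has complications followed by telephone without limiting this to group B. The *not* in the second sentence may be a translation slip, since the sentence is garbled in other ways. The documents cannot confirm this, and as written the two sentences still conflict.

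Several stronger readings are tempting, and the documents do not support them:

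- *Toxicity cannot be compared between groups.* It can be, from the recorded events. The plan simply does not specify the comparison.
- *Only side effects are indexed.* Unplanned rehospitalization is the second index, applies to both groups and needs no attribution.
- *The contradictory definition governs index 1.* No section ties side effects to the adverse-reaction definition. The contradiction and the undefined index are two separate faults.
- *Group A is zero by construction.* This holds only on the Summary's use of the term. Section 6 speaks of any drug or special formula. Both groups may receive chemotherapy, immunotherapy and megestrol, and group A may receive nutrition supplements.
- *The count swings from 0 to 23–46.* This is an outer bound under an assumed rate and an extreme attribution, not an estimate.

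What remains is a self-contradictory rule, an undefined main safety index whose nearest usage points to attribution, and no stated by-group tabulation. Recording events does not commit the sponsor to comparing them: the follow-up schedule in section 3 has no adverse-event row, and section 9 has no method for proportions.

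**Conclusion.** The point holds in limited form and should be corrected before the safety data are analysed. The contradiction in section 6 is certain from the text. That index 1 depends on attribution and lacks a control rate is conditional on the Summary's meaning of side effects. The plan supports more than one meaning, which is itself the fault. Index 2 does not fill the gap, because nausea, vomiting, diarrhoea or spasm managed without admission would not appear in it.

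The documents give no event rate from which to fix the size. The 23 to 46 patients per group rest wholly on the assumed 30% to 60% and show only that the classification could matter.

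A reader might infer that an all-event comparison would show whether the products cause harm. It would not do so by itself. Patients choose their group and know what they take, so any difference is descriptive and may reflect who chose the products or how symptoms were reported.

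**What to change.** 1. In section 6, reconcile the two adverse-reaction sentences so that both require at least a possible causal relation, and correct the wording on expectedness.
2. In section 5(4), define index 1 as the incidence and severity of all adverse events in both groups, regardless of attribution. Use the same window in each group, from enrolment to the end of follow-up, and name the severity scale.
3. Show nausea, vomiting, diarrhoea, and muscle stiffness or spasm separately by group.
4. In section 9, add a method for proportions: the risk difference with a 95% confidence interval, or Fisher's exact test.
5. Report events judged related to the study products in group B as a second line, labelled as open-label attribution.
6. State that the comparison is descriptive because allocation follows patient choice.

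The cost is wording in sections 5(4), 6 and 9 and one summary table. It uses events that sections 6 and 8 already require to be recorded. The reported rate may look less favourable, since events caused by cancer treatment will be included in both groups.

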1.3 Research to be carried out.

In this review, cachexia is a common complication of various advanced malignant tumors, which seriously affects the quality of life and survival time of patients. In view of the clinical problem of non-nutritional response in patients with cachexia, we plan to carry out a clinical case-control study on the intervention of creatine combined with curcumin in patients with cachexia. Overall, we limited the study subjects to upper digestive tract tumors and diagnosed patients with early cachexia. The main purpose of this study is to determine whether the combination of the two can play a positive and stable role in inhibiting the inflammation of cachexia and improving metabolic status, so that basic nutrition can play a role, to reduce the level of skeletal muscle consumption, maintain weight, improve quality of

life, save medical costs, and extend survival time.

2. Purpose of the study

(1) To investigate whether creatine combined with curcumin can improve the inflammatory state, correct the disorder of nutrient metabolism and improve the nutritional status in the early cachexia stage of upper gastrointestinal neoplasms.

(2) To investigate whether creatine combined with curcumin can improve the quality of life and prognosis of patients with early cachexia in upper digestive tract tumors.

3. Study design type, principle, and test procedure

(1) Study Design

Type of study design: prospective open controlled clinical trial; Non-random grouping method: According to the exclusion criteria, patients were included into group A or group B according to their wishes after informed consent; Blind level: This experiment is an open study without blind or emergency letters. Research Center: None.

Group A: basic nutrition treatment, energy 30-35 kcal/kg, protein 1.0-2.0 g/kg, diet deficiency, total nutrition and/or whey protein oral nutrition supplement or tube feeding enteral nutrition supplement.

Group B: Since basic nutrition in group A, creatine 5g/d and curcumin 4g/d were orally added, and the intervention time was 1 month.

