It was assumed that after 4 weeks of oral administration of creatine + curcumin in group B, combined with the existing literature on the improvement of the quality of the bad fluid, the skeletal muscle index at L3 section of CT scan in group B was 20% higher than that in control group A, and the standard deviation was 14%. Bilateral test was required, α was 0.05, the sample ratio between the two groups was 1:1 (i.e., the number of cases in the two groups was equal), $\beta=0.2$. The degree of assurance (test efficacy) $1-\beta=80\%$ was calculated using SPSS software, then the sample size of each group was 68 cases, considering the 10% loss of follow-up rate, each group needed 76 cases, 152 patients in total.

Follow-up test item time point

Classification	Item	0	0.5m	1m	3m
Serological indicators	blood routine	√	-	√	√
	biochemical set	√	-	√	√
	prealbumin	√	-	√	√

	transferrin	√	-	√	√
Body composition index	CT scans skeletal muscle index at L3 cross section	√	-	√	√
	BIA measures muscle mass	√	-	√	√
Inflammatory metabolic indicators	Serum insulin	√	-	√	√
	IL-6	√	-	√	√
	TNF- α	√	-	√	√
	lactic acid	√	-	√	√
	PETCT (SUV)	p.r	-	p.r	-
Physical measurements	Weight	√	√	√	√
	grip strength	√	√	√	√
	skin fold thickness	√	√	√	√
	upper arm circumference	√	√	√	√
nutrition assessment	intake	√	√	√	√
	PG-SGA score	√	√	√	√
Questionnaire Survey	Functional Assessment of Anorexia/Cachexia Therapy(FAACT)	√	√	√	√
	ADL evaluation scale	√	√	√	√

4. Criteria

Inclusion Criteria:

(1) Clinical diagnosis of advanced tumors of the upper digestive tract with untreatable or postoperative recurrence of esophageal and gastric cancer III-IV

- (2) Meet the diagnostic criteria of early cachexia (anorexia and metabolic changes, involuntary body mass reduction $\leq 5\%$ within 6 months)
- (3) Radiotherapy, chemotherapy, or immunotherapy in our hospital
- (4) Understand and fill in a variety of rating scales
- (5) Informed consent, voluntary participation in this study

Exclusion Criteria:

- (1) Neoadjuvant chemotherapy patients
- (2) Intestinal obstruction or gastrointestinal bleeding
- (3) Severe heart, lung and renal insufficiency
- (4) Coagulopathy
- (5) Clinical diagnosis with diabetes and other metabolic diseases
- (6) The expected survival time is less than 1 month
- (7) With cognitive dysfunction or poor coordination
- (8) Allergy to creatine or curcumin
- (9) With a history of drug abuse
- (10) Doctors or researchers deem unsuitable for study participation

Removal Criteria:

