- (1) Do not meet the inclusion criteria and mistakenly included or meet any of the exclusion criteria.
- (2) Meet the inclusion criteria but did not use after inclusion or did not have any record of return visit.
- (3) The intervention measures used during the trial did not conform to the protocol.

Criteria for study termination:

- (1) With allergic reactions or serious adverse events should be stopped according to the investigator's judgment.
- (2) Other complications and special physiological changes occurred during the test.
- (3) During the experiment, the subjects needed parenteral nutrition support during the nutritional support process, and the experiment should be stopped.
- (4) Poor compliance.
- (5) Pregnancy.

5. Research methods and technical route

(1) Research food names and specifications

The creatine provided to the patient in this experimental study scheme was purchased from the sports nutrition food Decathlon creatine powder (powder: 10g/ packet *10 packets/box) produced by Jiangsu Alante Nutrition Co., LTD. Purchased from Meriva Curcumin Phytosome (capsule: 1g/ capsule *120 capsules/box) from THORNE Company, USA.

(2) Treatment plan

Clinical data of patients with advanced esophageal and gastric cancer combined with early cachexia were collected, abdominal CT scan was performed, and the skeletal muscle area and

density of L3 section were measured by Matlab software. Skeletal muscle index was obtained after height correction, and body composition and bone mineral density were measured at the same time. Routine examination and nutritional indexes were determined, including blood routine, biochemical set, prealbumin, transferrin; Inflammatory metabolic markers including serum insulin, IL-6, TNF- α , lactic acid, and PETCT were assessed for metabolism. NRS2002 and PG-SGA scores were performed. According to the standard body weight, dietitians formulated diets for all enrolled patients. According to the ESPEN guidelines and the national industry health standard "Dietary Guidelines for Patients with Malignant Tumors 2017", the dietary energy intake standard was 30-35kcal /kg·d, and the protein intake was 1.0-2.0g /kg·d. The deficiency was given to oral enteral nutrition supplements or whey protein supplements, or to patients requiring tube feeding. Patients were enrolled in group A control group or group B intervention group on a voluntary basis.

Group A intervention group: The above basic nutritional support was provided.

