The clinical study will develop a data safety monitoring plan according to the risk. All adverse events are recorded in detail, properly handled and tracked until properly resolved or the condition is stable, and serious adverse events and unexpected events are reported to the Ethics Committee, competent authorities, sponsors and drug regulatory authorities in a timely manner in accordance with regulations; The principal investigator conducts regular cumulative reviews of all adverse events and holds investigator meetings where necessary to assess study risks and benefits; For studies with greater than minimum risk, an independent data monitor will be assigned to monitor the study data. For high-risk studies, an independent Data Safety Monitoring committee will be established to monitor the accumulated safety and efficacy data and make recommendations on whether to proceed.

9. Statistical analysis

Statistical analysis was performed using GraphPad Prism version 8.0 (La Jolla, CA, USA). Student's t-test was used for comparison between groups, and one-way analysis of variance (ANOVA) was used for other data. All data are presented as mean \pm SEM. $p < 0.05$ (*) indicates statistical significance. $p < 0.01$ (**) indicates that the difference is more statistically significant.

10. The ethics of clinical research

Clinical research will follow the relevant regulations such as the Declaration of Helsinki of the World Medical Congress. Clinical studies are conducted only after the protocol is approved by the Ethics Committee prior to the start of the study. Before each subject is enrolled in this study, the investigator is responsible to give a complete and comprehensive introduction of the purpose, procedure and possible risks of this study to the subject or his/her agent and sign a written informed consent. Subjects should be informed that they have the right to withdraw from this study at any time, and informed consent should be kept as a clinical study document for future reference. Subjects' privacy and data confidentiality will be protected during the study.

11. Research schedule

Jun 1,2023 to Aug 31,2023: The formal implementation of the project was started. 76 cases were collected, and baseline investigation was conducted for enrolled patients. The patients were not randomly enrolled, and grouped intervention was performed.

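### Self-chosen groups are compared by an unadjusted t-test although baseline values are collected, and tumour response and incomplete survival follow-up have no suitable method

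*Combined protocol and SAP*

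**What the plan says.** Section 9, repeated in the Summary under Method of statistics, states: "Student's t-test was used for comparison between groups, and one-way analysis of variance (ANOVA) was used for other data". It adds mean ± SEM for all data and two p-value thresholds. It names no covariate, no analysis time point and no outcome scale.

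The other relevant statements are these.

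- **Allocation** (section 3 (1); also the Summary and section 5 (2)): "patients were included into group A or group B according to their wishes after informed consent". The study is open.
- **Baselines** (section 3, follow-up table): the month-0 column is ticked for the serum, inflammatory, body-composition, physical, nutritional and questionnaire measures, including "CT scans skeletal muscle index at L3 cross section". PET-CT is the only item without a regular tick.
- **Sample size** (section 3): after 4 weeks the L3 index "in group B was 20% higher than that in control group A, and the standard deviation was 14" per cent, with 68 per group before loss to follow-up.
- **Concomitant treatment** (section 5 (3)): "During the study period, patients may have been treated with chemotherapy drugs and immunotherapy drugs due to tumor treatment", and "the diseases, and drugs of the two groups will eventually be grouped and stratified to eliminate the interference of combined drug use".
- **Secondary indicators** (Summary): these include 1- and 3-month survival rates and tumour remission and progression.
- **Removal Criteria (2)** (section 4): these cover patients who, after inclusion, "did not have any record of return visit".
- **Telephone contact** (section 5 (2)): "The intake, complications and survival of the patients were followed up by telephone for 1 and 3 weeks".

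**The concern.** In a randomised trial an unadjusted t-test is valid, if not the most precise choice. Here patients decide which group they join, so those who choose the supplements may differ at the start in muscle mass, nutrition or disease. An unadjusted test passes such a difference into the result. If the groups differ at baseline, the 4-week comparison and the change comparison give estimates that differ by exactly that gap, and section 9 does not choose between them.

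The stratification in section 5 (3) has no stated strata or method, is not carried into section 9, and covers diseases and drugs but not the baseline values of the outcomes. It also concerns drugs used during the study, some of which may be started after grouping.

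The prognosis objective relies on survival and tumour response. Remission and progression are categories, for which a t-test, one-way ANOVA and mean ± SEM are unsuitable. Survival needs a rule for patients lost to follow-up, and section 9 has none. The data left to one-way ANOVA are undefined. If they include repeated visits of the same patients, that test wrongly treats the visits as independent.

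**Working it through.** **Inputs from the plan.** Two-sided alpha 0.05, 1:1 groups, 68 per group. The loss step reproduces: 68/0.9 = 75.6, so 76 per group and 152 in total. The stated 20% and 14% give 20/14 = 1.43 SD, for which a t-based calculation needs 9 per group, not 68; 68 corresponds to about 0.484 SD. That mismatch is a separate matter, and 68 is used here only as the number analysed.

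**Assumed inputs**, because the documents give neither: a baseline gap g of 0.3 SD (0.2 SD as a check) and a baseline/4-week correlation r of 0.3 to 0.9. The upper end is included because a CT muscle index re-measured after 4 weeks may correlate highly. SD is 1 at both times, and there is no treatment effect.

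**Case 1: the outcome's own baseline is the only confounder** (4-week value = r × baseline + error).

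- 4-week values: bias r·g, noncentrality r·g·√(n/2), with √(68/2) = 5.831. At r = 0.5: 0.5 × 0.3 × 5.831 = 0.875, rejection 14.0%.
- Change: bias −(1−r)·g, SD √(2(1−r)). At r = 0.9: 0.1 × 0.3/√0.2 × 5.831 = 0.391, rejection 6.7%.
- ANCOVA: bias 0.

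**Case 2: the gap is a stable difference that would persist anyway** (4-week means also differ by g).

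- 4-week values: 0.3 × 5.831 = 1.749, rejection 41% at every r.
- Change: bias 0.
- ANCOVA: bias (1−r)·g, residual SD √(1−r²), standard error factor √(2/n + g²/(2n−2)). The noncentralities are 1.27, 1.00, 0.73 and 0.40.

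False-positive rates at g = 0.3:

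| Analysis | r = 0.3 | 0.5 | 0.7 | 0.9 |
|---|---|---|---|---|
| Case 1, 4-week value | 8% | 14% | 23% | 35% |
| Case 1, change | 18% | 14% | 10% | 7% |
| Case 1, ANCOVA | 5% | 5% | 5% | 5% |
| Case 2, 4-week value | 41% | 41% | 41% | 41% |
| Case 2, change | 5% | 5% | 5% | 5% |
| Case 2, ANCOVA | 24% | 17% | 11% | 7% |

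Simulation with 20,000 trials per cell agrees to within about one percentage point. At g = 0.2, case 1 gives 6%, 9%, 13%, 18% on 4-week values and 11%, 9%, 7%, 6% on change.

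**Sign.** In case 1 with true effect τ and a gap favouring B, the 4-week estimate is τ + r·g and the change estimate is τ − (1−r)·g. With g = 0.3 they have opposite signs only if τ is below 0.21, 0.15 or 0.09 SD at r = 0.3, 0.5, 0.7. With the gap reversed, the limits are 0.09, 0.15 and 0.21 SD.

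**Survival, illustrative counts for one group of 76.** With 6 deaths by month 1, 3 of them before any visit, survival is 70/76 = 92.1%. If those 3 are removed it reads 70/73 = 95.9%. With 2 deaths, 1 of them early, 74/76 = 97.4% becomes 74/75 = 98.7%.

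**The case against.** *The sample-size paragraph already fixes the comparison.* It does point to 4-week values for the L3 index. It remains a planning assumption for one outcome, and a test on 4-week values alone is still exposed to the baseline gap.

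*Preferring ANCOVA is a matter of taste.* This stands in part. Against the change score, ANCOVA is better in case 1 and worse in case 2, and nothing in the documents says which case applies. Against the unadjusted 4-week test, ANCOVA has the lower error in both cases at every r shown.

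*Power is ample.* At 1.43 SD unadjusted power exceeds 99.99%, so adjustment adds no power there. The argument rests on bias, which power does not cure.

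A reader might also infer more than the documents support:

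- *That the direction of the result hangs on the choice of scale.* It does so only when the true effect is small. At 0.484 SD both estimates stay positive for r of 0.3 to 0.7.
- *That group differences are ignored altogether.* Section 5 (3) does intend stratification; what is missing is the method and the outcome baselines.
- *That survival has no usable estimate.* The mean of a 0/1 variable is a proportion. With 76 per group and survival of 80 to 95%, a t-test on 0/1 data rejected 4.1 to 5.1% of the time under no difference. This holds only with complete follow-up.
- *That early deaths will be dropped.* This follows only if a return visit excludes the telephone contacts, which the text does not settle. The counts above are assumed and for one group, so they show no between-group bias.

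**Conclusion.** The concern holds for three things: the unadjusted comparison of self-chosen groups, the absence of a valid method for tumour response, and the absence of a survival method that allows for loss to follow-up.

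Under an assumed 0.3 SD gap with the outcome's baseline as the only confounder, the error rate is 8 to 35% on 4-week values and 7 to 18% on change, against 5% with ANCOVA. The gap and the correlation are assumptions, so these figures show sensitivity and do not forecast what the trial will find. If the gap is a stable difference, ANCOVA errs at 7 to 24% and change at 5%. Neither adjusted analysis removes all confounding from self-selection, and unmeasured factors remain in any case.

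The points on one-way ANOVA for repeated visits and on removal of early deaths are conditional on how the undefined wording is read. The plan should settle both. This should be corrected before analysis.

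**What to change.** In section 9, and in the matching Summary entry:

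1. For continuous outcomes, replace the t-test by ANCOVA of the 4-week value on group, the outcome's baseline value and a list, fixed in advance, of baseline disease and treatment factors. The Summary's baseline investigation already records stage, complications, treatment, treatment stage and drug use. Report the group difference with a 95% CI. Pre-specify the change-score analysis as a sensitivity analysis, and state that confounding from self-selection may remain.
2. State that the stratification in section 5 (3) is limited to factors present at baseline. This modifies section 5 (3), which refers to drugs used during the study, and the text should say so.
3. Define which data one-way ANOVA was meant for. If they include repeated visits, use a repeated-measures model.
4. Report tumour response and progression as counts and percentages, compared by Fisher's exact test or logistic regression.
5. Report 1- and 3-month survival by Kaplan-Meier, with the group difference and 95% CI. Keep every enrolled patient with known vital status, telephone contact included, and reconcile Removal Criteria (2) with this.

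The cost is SAP wording and slightly more modelling. No new data or visits are needed.
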